It is known that poor adherence to pharmacological treatment and medical advice is a global problem and is particularly important in chronic diseases(110). Historically the core treatment for CF was symptom management often involving complex pharmacological treatments that become extensive with increasing age. When viewed in combination with other required treatments such as physiotherapy, it is perhaps unsurprising that many people with CF report significant time burdens associated with daily treatments (111). Adherence is defined as "the extent to which a person's behavior - taking medication, following a diet and/or executing lifestyle changes - corresponds with agreed recommendations from a healthcare provider". Adherence in CF is suboptimal, and poor adherence has been linked to an increased burden of illness and greater healthcare costs(112, 113). Parents or guardians exhibit greater responsibility of treatment in younger children, whilst in adolescence parental influence reduces. By the time patients are transitioning to adult services, adherence may have reduced by 50%(112). Despite the well-known disease-modifying benefits of the already licensed CFTR modulator lvacaftor, studies have found adherence to be suboptimal (114, 115).

P.I. [name]

Self-reporting is the most widely used method for measuring medication adherence due to ease of implementation and low cost. The limitations of self-reporting are that the patient can often over estimate adherence or fail to disclose non adherence due to recall bias (116).

A second method is medication pick-up rates which can identify patients at risk for treatment failure (117). This information is usually extracted from the computerized system in community pharmacies. A limitation is that it measures maximum possible adherence.

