No single method fulfils the criteria for an optimal medication adherence monitoring and therefore multiple methods are often employed (118). A recent study examining this issue in individuals with CF taking Ivacaftor used multiple methods for measuring adherence, however had a small sample size (n=12). Adherence to Ivacaftor by Self-report was 100%, by pharmacy refill data (medication possession ratio)was 84% and using the gold standard of electronic monitoring MEMS® (medication event monitoring system) was 61%(115). The study was unable to measure the impact of the non-adherence. To our knowledge, there are no published longitudinal studies examining the effect of CFTR modulators on adherence to CF treatment regimens and associated clinical outcome measures.

Although the incidence of CF is low, the cost of illness can be substantial. In 2015, the National Centre of Pharmacoeconomics (NCPE) of Ireland compared CFTR modulator treatment with standard of care and estimated an incremental quality-adjusted life-years (QALY) gain of 2.45 at an incremental cost of €903,947.(119) With this significant costs comes a responsibility in the CF community to understand both modulator and overall medication use in the real world and determine what effect this might have on outcomes.

Genetic Modifiers of Treatment Response

CF is a disease area where considerable work has focused on the non-CFTR factors involved in disease phenotype heterogeneity. Modifier genes have been discovered relating to several different aspects of the CF phenotype including lung function, lung disease severity and abdominal and endocrine manifestations of CF(120). Our collaborator [name] at SickKids Toronto has a specific interest in genes that modify the CF phenotype. His team have recently shown that certain modifier genes also affect the response to CFTR directed therapies such as Ivacaftor and lumacaftor. We are therefore very interested in studying these modifier genes in people with CF initiated on highly effective CFTR modulator therapies. **RECOVER represents an ideal opportunity to link the genotypic findings to in vivo drug response which will be monitored closely within the study.** Our collaborators at SickKids have the laboratory technologies in place and have secured funding for the genotyping which can occur as part of a Genome Canada funded project at any time when DNA samples will become available.

A New Era for CF Treatment

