We will undertake a detailed assessment of adherence as part of RECOVER so that we can link our findings in relation to treatment adherence to important disease outcomes. The treatment adherence arm of RECOVER will be led by [name], a clinical pharmacist at CHI Crumlin, who will undertake a five-year, part time PhD with RECOVER as the central theme. Prescribed medications at an individual level will be tracked throughout the study to ensure we have a reliable denominator on which to base adherence measures. A number of methods will be used in RECOVER to monitor and understand treatment adherence in the real-world setting:

- Electronic medication event tracking systems e.g. (MEMS®)
- Self-reported adherence
- Medication possession ratio (MPR) based on pharmacy pick up rates
- Qualitative assessment of beliefs and attitudes around adherence to ETI and other treatments

Medication Event Monitoring System (MEMS®)

This is the gold standard for electronic monitoring but can only measure monotherapy. It mimics a traditional pill bottle with the enhanced ability to track the date and time of each bottle opening.(92) Non adherence to MEMS® is less likely as the adherence pattern is recorded by the opening of the container for every dose. Therefore, it is used as a reference standard for validating other reference tools.(92) This data can be used to calculate the medication possession ratio per patient. Due to the high cost and additional support required this method of measuring adherence is under-utilized. We will measure adherence to ETI with MEMS® in a subset of RECOVER subjects in the Dublin Centres (approximately 100 individuals). MEMS® will not be used for adherence measurements with treatments other than ETI.

Parent/Subject Self-reporting of Adherence

This will be carried out using the up to date version of a specifically designed adherence scale for children and adults with CF(145) with the permission of the author [name] (a RECOVER collaborator). The treatment adherence questionnaire, barriers to adherence questionnaire and prescribed treatment plan will be used to monitor self-reported adherence.

Treatment Burden

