The CFQ-R treatment burden subscale, part of the CFQ-R questionnaire, has been used to assess treatment burden in people with CF(113). The treatment burden subscale, which comprises 3 questions, is scored on a standardized 0- to 100-point scale with lower scores representing a higher treatment burden. The questions are as follows: to what extent do your treatments make your daily life more difficult? How much time do you currently spend each day on your treatments? How difficult is it for you to do your treatments each day? CFQ-

Medication Possession Ratios

protocol in table 14.

MPR will be calculated using pharmacy records. MPR is calculated on the basis of the supply of medications for a given period divided by the time in that period. For example, if three scripts for 3 months of a treatment are given over a timeframe of one calendar year, the MPR would 0.75. MPR will be calculated for each individual medication for each study participant. Study consent will be sought for dispensed reports from hospital pharmacy, community pharmacy and homecare providers and GP medical records to be submitted to the subject's center at the end of the study period. Records will be analyzed locally and data on antibiotic use, enzyme use and MPRs per 6-month period calculated by the local study team before being uploaded in an anonymized fashion to the study database.

Qualitative Assessment

Using a combination of previously published data(146), adherence theory (e.g. WHO five dimensions of adherence) as well as the findings of the observational research, a semi-structured interview guide will be designed. Using the same cohort invited to participate in the MEMS component of the study, 20-40 participants will be interviewed with interviews halted when data saturation is achieved. Only subjects from the Dublin centers will be invited to participate for ease of access (the adherence lead for RECOVER is based in Dublin). These data will be analyzed using a qualitative analysis plan involving phenomenography/thematic analysis with constant comparative analysis to the WHO adherence framework. Through this process we hope to be able to explore the experiences of patients/parents on commencement of CFTR modulator and adherence to CF regimens. We hope to be able to establish individual factors that influence adherence in this 'new world' for this large cohort of people with CF.

Data Analysis

Analysis of data will be conducted as follows based on our key research questions:

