• What level of adherence with ETI is seen in the real world?

Measures of weekly adherence (using the three measures independently) will be reported and compared to previously published data on adherence rates with Ivacaftor(115, 147). Adherence over time, using all three methods, will be reported in a weekly fashion as treatment progresses. Changes in adherence over time (weekly, quarterly) will be assessed per individual and cross sectionally. We will explore the relationship between weight gain and subsequent adherence to ETI (because of concerns on behalf of some PWCF about excessive weight gain on modulators).

• Does adherence with other CF therapies decrease after ETI?

Adherence rates, using MPR and self-reported adherence, to medications individually and in groups (vitamins, mucolytics, nebulized antibiotics etc.) will be collected from 3 months prior to the introduction of ETI. The absolute change in adherence for 4 quarters (one before and three after) will be compared using chi squared and ANOVA. The rate of change of weekly adherence will be compared prior to and in the 9 months after (in 3 quarters) initiation of ETI using ANCOVA.

• Does poor adherence adversely affect outcomes?

This question will be addressed from the point of view of firstly, adherence with ETI, and secondly, adherence with other groups of medications. Medium term effects will be determined by comparing overall 12 and 24-month MPRs for given medications and groups of medications and specific relevant outcome measures such as CT scores, LCI, FEV1, nutritional status, antibiotic use and exacerbations at the end of 12 and 24 months respectively.

• Is adherence related to treatment burden?

Results from the various adherence measures will be compared, within individuals, to the CFQ-R treatment burden subscale results at each timepoint.

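### The analysis of whether poor ETI adherence worsens outcomes names only the pharmacy possession ratio and leaves out the MEMS readings taken at the same time points in about 100 participants

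*Protocol*

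**What the plan says.** The operative text is in the Protocol, Specific Aim 7 for Parent Study, Data Analysis, under the question on whether poor adherence affects outcomes. It sets the order of exposures: "This question will be addressed from the point of view of firstly, adherence with ETI, and secondly, adherence with other groups of medications". It then names the measure: "Medium term effects will be determined by comparing overall 12 and 24-month MPRs for given medications and groups of medications", to be set against CT scores, LCI, FEV1, nutritional status, antibiotic use and exacerbations at 12 and 24 months. MEMS is not mentioned there.

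Other parts of the protocol bear on that choice:

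- Aim 7, Medication Possession Ratios: "MPR will be calculated using pharmacy records". The ratio is supply divided by time.
- Background, Treatment Adherence, on pharmacy pick-up: "A limitation is that it measures maximum possible adherence". The same section reports that, in 12 people on ivacaftor, adherence "by pharmacy refill data (medication possession ratio)was 84% and using the gold standard of electronic monitoring" was 61%.
- Aim 7, Medication Event Monitoring System: MEMS is described as the gold standard and as the reference for validating other tools. It will be used for ETI "in a subset of RECOVER subjects in the Dublin Centres (approximately 100 individuals". The same paragraph adds that MEMS data can be used to calculate a possession ratio.
- Table 14: MEMS readings and pharmacy MPR records are both scheduled at months 12 and 24.
- The neighbouring Aim 7 questions are wider. The level of ETI adherence is described with all three measures separately, and treatment burden is compared with the various adherence measures.

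**The concern.** A possession ratio built from supply cannot separate tablets taken from tablets collected and left. For ETI, the people who collect but do not take are the poor adherers whose outcomes the question is about, and MPR scores them as adherent. The protocol sees this mechanism elsewhere: under Risks with Exacerbation Data Collection it expects pharmacy records to overstate antibiotic use, because some courses are collected but not taken.

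If the resulting error varies from person to person, the association between ETI adherence and outcome is weakened, and a null finding could partly reflect measurement. If the error instead squeezes the range of MPR, the estimated effect per unit of adherence can be too steep. Either way the MPR analysis cannot show which has happened. The protocol remarks that the earlier ivacaftor study could not measure the impact of non-adherence. RECOVER will hold data that could, but the stated analysis does not call on them.

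**Working it through.** The protocol gives no power, effect size or sample size for this analysis, so there is no design figure to reproduce. Its worked MPR example is correct: three 3-month supplies in a year give 9/12 = 0.75. On the same formula, a person who collects all twelve months scores 12/12 = 1.00 however much is taken.

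**Step 1. What the cited figures show.** The gap is 84 - 61 = 23 percentage points, and the ratio is 84/61 = 1.38. This is a difference between two means, in 12 people on a different modulator. It says nothing about how MPR and MEMS move together across people.

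**Step 2. Whether a mean gap implies dilution.** Simulation of 1,000,000 draws. Assumptions, not in the documents: MEMS adherence is beta-distributed with mean 0.61, and outcome = 1.0 x MEMS + normal error with SD 0.8. Every error model below is set to give mean MPR 0.84.

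| Exposure | Slope | Correlation with outcome | Correlation with MEMS |
|---|---|---|---|
| MEMS itself | 1.005 | 0.264 | 1.00 |
| Uniform shift of +0.23 | 1.005 | 0.264 | 1.00 |
| Shift capped at 100% | 1.202 | 0.254 | 0.964 |
| Shortfall shrunk in proportion (factor 0.16/0.39 = 0.41) | 2.449 | 0.264 | 1.00 |
| Random share of each person's shortfall added | 0.807 | 0.151 | 0.576 |

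All four MPR models match 84% against 61%, yet they run from no distortion, through a slope that is too steep, to clear dilution. The cited means cannot tell them apart.

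**Step 3. Power.** If MPR relates to outcome only through MEMS adherence, then

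observed r = true r x corr(MPR, MEMS)

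Power at an assumed two-sided 5% level is approximately Phi(atanh(r) x sqrt(n - 3) - 1.96). For MEMS with r = 0.30 and n = 100: 0.3095 x 9.849 - 1.96 = 1.09, so power is 0.862. The 254 is the recruitment cap in Sample Size and Power. The true r and the MPR-MEMS correlations are assumptions.

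| | True r = 0.2 | True r = 0.3 |
|---|---|---|
| MEMS, n = 100 | 0.515 | 0.862 |
| MPR, N = 254, corr 0.3 | 0.158 | 0.298 |
| MPR, N = 254, corr 0.5 | 0.356 | 0.668 |
| MPR, N = 254, corr 0.63 | 0.519 | 0.858 |
| MPR, N = 254, corr 0.8 | 0.725 | 0.972 |

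The crossover is where the larger sample just offsets the attenuation: sqrt(97/251) = 0.622, or sqrt(100/254) = 0.627 without the Fisher correction. With 201 participants it is about 0.70.

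**The case against.** Several objections carry weight.

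- A reader might infer from 84% against 61% that a real effect will be diluted. The documents do not support that. As the simulation shows, a uniform overestimate leaves the association intact and proportional compression steepens the slope. Only error that varies between people dilutes, and the protocol gives no figure for it.
- A reader might also infer that MEMS should replace MPR as the ETI exposure. That does not follow either. MEMS covers only about 100 Dublin participants and excludes Limerick, Belfast and London. CT is done only in the advanced group (150 planned in Table 6), so fewer MEMS users may have CT scores. Above a correlation of about 0.62-0.63, MPR in 254 people has more power.
- The limitation is disclosed: the Background and the closing paragraph of the Aim 7 analysis section both admit that MPR is imprecise. MPR is also the natural common measure for a sentence that covers all medications.
- The Aim 7 introduction speaks of linking adherence to outcomes in general, and the CT and antibiotic sections refer to adherence without naming a measure. The remark that MEMS data can yield a possession ratio leaves room for a MEMS-derived MPR. That remark is permissive and is not a firm contradiction of the pharmacy definition, but it leaves the term unclear.
- Exposure definitions and calibration are often left to the SAP, which is not at hand.

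The last objection does not dispose of the point. The protocol does not leave the measure open here: it names one, and names only the weaker one, while the neighbouring questions call on all three or on the various measures. Disclosing a limitation is also not the same as using the data that could correct it.

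**Conclusion.** The point holds as a cheap improvement to a stated method. For the ETI part of the adherence-outcome question, the protocol names only a supply-based measure that it describes elsewhere as an upper limit. It does not name its own reference measure, although that is read at the same months in about 100 people. The association may be diluted or its slope distorted, and neither the direction nor the size can be known from the documents. In the four models tried, the MPR-outcome correlation ranged from unchanged (0.264) to 0.151, and the slope from 0.81 to 2.45 against a true value of 1.0. Those ranges rest on the assumed distributions and show what is possible, not what is expected. The power comparison likewise rests on an assumed true correlation, an unknown MPR-MEMS correlation, and full outcome data in all 100 MEMS users. Adding MEMS beside MPR is justified under any of the models; demoting the full-cohort MPR analysis is not.

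**What to change.** In the Aim 7 Data Analysis text on outcomes, for the ETI part:

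1. Relate MEMS adherence (the share of prescribed dosing occasions with a recorded opening, over months 0-12 and 0-24) to the listed outcomes in the MEMS subset.
2. Report this beside the full-cohort ETI MPR analysis, with neither replacing the other.
3. Use participants with both measures to calibrate MPR, for example by regression calibration, and report the MPR-MEMS correlation.
4. Keep MPR for the other medications, which MEMS does not cover.
5. State that MPR means the pharmacy-supply ratio, and give any MEMS-derived figure a different name.

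The cost is wording and some added analysis, since both measures are already scheduled. The downside is limited precision and reach: the MEMS analysis rests on about 100 Dublin participants, with fewer for CT.

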In exceptional circumstances where baseline clinical data has been collected prior to the start of treatment either through clinical care or ethically approved research projects (including a cohort of subjects initially recruited to this study on the understanding that it was a non-regulated observational study) subjects already receiving ETI may be recruited to this study and undergo on-treatment visits. Any additional patient data can only be added with written informed consent from the patients/parents concerned.

P.I. [name]

All subjects must have a signed informed consent form and/or signed assent form when appropriate, as determined by the subjects age and individual site and country standards.

Male and female participants of childbearing potential must agree to adhere to contraception requirements as detailed in the local ETI SmPC and in line with the standard of care.

Exclusion criteria

Patients not willing to comply with study procedures or assessments.

Individuals on clinical trials of investigational CFTR modulators.

Clinical instability at baseline assessments. Subjects undergoing an active exacerbation and at the beginning of their treatment should be excluded from the study as this is likely to skew the data.

Any contraindication to ETI treatment as per the local approved SmPC.

Severe hepatic impairment.

Pregnant and breastfeeding women.

Inclusion and Exclusion Criteria for Extension Study

Inclusion criteria

Children and adults with CF who have completed two years participation on the parent study, and are willing to provide informed consent for continued data and bio-sample collection for a period of five years.

Exclusion criteria

Participants not willing to comply with study procedures or assessments.

Individuals on clinical trials of investigational CFTR modulators.

Drug Interruption or Discontinuation of ETI

If a patient experiences a drug interruption, discontinues ETI and/or is prescribed TEZ/IVA, LUM/IVA or IVA, they can continue trial participation.

Advanced Testing v Standard Testing for the Parent Study

As outlined in Table 5, we will have a standard and advanced testing group for the parent study. In addition to all elements of the standard testing group, the advanced testing group will undergo:

- Ultra-low dose spirometry-controlled CT scanning
- Sputum collection
- Nasal lavage collection

Table 6 outlines projected recruitment targets for both groups. Advanced testing will be offered to all participants to the cap in table 6, on the basis of fully informed consent. Progress in recruitment to both groups will be monitored by the project manager and monitor.

	F/F		F/M		F/G		TOTALS		S
	6-		6-		6-		6-		
Ages	11	12+	11	12+	11	12+	11	12+	All
ADVANCED	47	60	17	26	17	0	64	86	150
STANDARD	27	36	9	15	0	0	36	51	87

Total 74 96 26 41 17 0 117 137 254	Total	74	96	26	41	17	0	117	137	254	
------------------------------------	-------	----	----	----	----	----	---	-----	-----	-----	--

Table 6. Projected recruitment to standard and advanced testing arms for parent study.

Primary and Secondary Outcomes

The primary outcome measure for this study is the absolute change from base line values and CT scores.

The secondary outcome measures are as follows;

- height/weight/BMI
- FEV1
- Airway microbial culture
- Airway microbiome determination
- Nasal Lavage inflammatory markers
- Nasal microbiome determination
- Exhaled Nitric Oxide
- Liver function testing
- Liver ultrasound Liver
- Examination score
- Sputum inflammatory markers
- Sputum microbiome determination
- Stool inflammatory markers
- Stool microbiome determination
- Sweat Chloride
- Genetic modifiers of CF phenotype
- Abdominal symptom score
- CFQ-R
- Treatment Adherence
- Medication Pick up rates

Core Data to be Collected

Eligibility assessment

Prior to study enrolment, the investigator will assess subject eligibility. This will include reviewing the subject's current medication and medical history in detail to ensure no exclusion criteria are met and all inclusion criteria are met. As part of the eligibility assessment, a urine pregnancy test (CE marked) must be conducted in female participants considered of childbearing potential (WOCBP). WOCBP are defined as females that are fertile, following menarche, until becoming post-menopausal unless permanently sterile. Permanent sterilisation methods include hysterectomy, bilateral salpingectomy and bilateral oophorectomy. A postmenopausal state is defined as no menses for 12 months without an alternative medical cause. A negative test must be produced prior to enrolment and documented within the subject's medical records.

Demographic data

Core demographic data will be collected on all individuals including genotype, sex, date of birth, CF centre and medications.

Sweat Chloride

Sweat tests will be carried out on all individuals prior to initiation of treatment and then at 6 months after treatment, at one year and at two years for the parent study, and annually in the extension study. Sweat will be collected using the Macroduct sweat collection system as per manufacturer's instructions using pilocarpine iontophoresis to induce sweating. Sweat tests will be performed on both arms. Sweat will be stored in 0.2ml

P.I. [name]

PCR tubes and immediately transferred to the laboratory and frozen at -80°C. Sweat chloride will be analyzed in all stored sweat samples in batches by the Chloro-check Chloridometer (EliTech Group Inc.) at all sites.

Nutritional Indices

Height and weight will be measured at three monthly intervals throughout the duration of the parent study at each out-patient visit, and annually during the extension study. Height, weight and BMI z-scores will be calculated from these measurements.

Patient Reported Outcomes – Respiratory Symptoms

CFQ-R (including the CFQ-R treatment burden subscale) will be administered to study participants every six months during the parent study and annually during the extension study. Scores in all domains of CFQR will be compared between baseline and follow up visits.

Investigational Medicinal Product (IMP)

The IMP for this trial is ETI (EU/1/20/1468/001). This IMP is licenced for use in the United Kingdom and will be administered to study subjects in line with the prescription and in line with the SmPC. To be enrolled in the Parent Study, all patients were prescribed ETI. The decision to implement treatment with IMP is made completely independently of the decision to enter subjects into the study. If a patient experiences a drug interruption, discontinues ETI and/or is prescribed TEZ/IVA (EMEA/H/C/004682), LUM/IVA (EMEA/H/C/003954) or IVA (EMEA/H/C/002494) after enrolment, they can continue trial participation. IMP will be dispensed in accordance with usual clinical practice (i.e. by hospital pharmacy/community pharmacy) and therefore no additional labelling, QP batch release or drug accountability is required.

Recording and reporting of adverse events and reactions

Definitions

Torm	Definition					
Term						
Adverse Event (AE)	Any untoward medical occurrence in a patient or clinical trial					
	subject administered a medicinal product and which does not					
	necessarily have a causal relationship with this treatment.					
Adverse Reaction (AR)	Any untoward and unintended response in a subject to an					
	investigational medicinal product which is related to any dose					
	administered to that subject.					
	This includes medication errors, uses outside of protocol					
	(including misuse and abuse of product)					
Important Medical	These events may jeopardise the subject or may require an					
Event	intervention to prevent one of the above					
	characteristics/consequences. Such events should also be					
	considered 'serious'.					
SUSAR	Suspected Unexpected Serious Adverse Reaction					
	A serious adverse reaction the nature and severity of which is					
	not consistent with the information about the medicinal product					
	in question set out:					
	(a) in the case of a product with a marketing authorization, in					
	the summary of product characteristics for that product,					
	(b) in the case of any other investigational medicinal product, in					
	the investigator's brochure relating to the trial in question.					

Recording adverse events

All AEs occurring during the study observed by the investigator or reported by the subject, whether or not attributed to the study medication, will be recorded on the Case Report Form and in the medical notes unless they are stated as non-reportable events, in which case they will not be recorded. AEs will be collected from the time of consent until the final study visit

Non-reportable adverse events

Certain clinical and laboratory events in cystic fibrosis have a high background incidence or are considered to be typical clinical features of cystic fibrosis and would not need to be reported. These include the following;

- Pulmonary exacerbations and hospitalizations due to pulmonary exacerbations.
- Clinical signs and symptoms commonly associated with pulmonary exacerbations (nasal congestion, nasal discharge, cough, sputum production, drop in lung function, wheeze, crackles, positive bacterial/fungal cultures)
- Clinical signs and symptoms commonly experienced by patients with CF in their normal daily routine (abdominal discomfort/distension, headaches, fatigue, malaise, clubbing, nasal polyps)
- Symptoms of known CF complications such as liver disease (rise in liver function tests), diabetes, sinusitis, constipation and distal intestinal obstruction syndrome (DIOS)

NOTE: Any of the above events deemed by the clinicians/ study investigators to be possibly related to the study drug or occurring to a disproportionate degree should be reported as an adverse event/serious adverse event.

Adverse Events of Special Interest

-Influenza is an adverse event of special interest, consistent with the risk management plan for Kaftrio. Occurrence of Influenza will be recorded as an adverse event or serious adverse event in every subject.

Assessments of Adverse Events

Each adverse event will be assessed for the following criteria:

Severity

Category	Definition
Mild	The adverse event does not interfere with the subject's daily routine, and does not require intervention; it causes slight discomfort
Moderate	The adverse event interferes with some aspects of the subject's routine, or requires intervention, but is not damaging to health; it causes moderate discomfort
Severe	The adverse event results in alteration, discomfort or disability which is clearly damaging to health

Causality

The assessment of relationship of adverse events to the administration of IMP is a clinical decision based on all available information at the time of the completion of the case report form. The following categories will be used to define the causality of the adverse event:

Category	Definition
Definitely:	There is clear evidence to suggest a causal relationship, and other possible contributing factors can be ruled out.
Probably:	There is evidence to suggest a causal relationship, and the influence of other factors is unlikely
Possibly	There is some evidence to suggest a causal relationship (e.g. the event occurred within a reasonable time after administration of the trial medication). However, the influence of other factors may have contributed to the event (e.g. the patient's clinical condition, other concomitant events).
Unlikely	There is little evidence to suggest there is a causal relationship (e.g. the event did not occur within a reasonable time after administration of the trial medication). There is another reasonable explanation for the event (e.g. the patient's clinical condition, other concomitant treatments).
Not related	There is no evidence of any causal relationship.
Not Assessable	Unable to assess on information available.

Expectedness

Category	Definition
Expected	An adverse event that is classed in nature as serious and which is consistent with the information about the IMP listed in the SmPC
Unexpected	An adverse event that is classed in nature as serious and which is not consistent with the information about the IMP listed in the Investigator Brochure (or SmPC if Licensed IMP)

The reference document to be used by the Sponsor (RCSI) to assess expectedness of the event against the IMP is the SmPC for:

ETI (EU marketing authorisation number EU/1/20/1468/001)

Seriousness

The Principal Investigator (PI) should make an assessment of seriousness as defined below:

A Serious Adverse Event (SAE) is any adverse event that:

- results in death,
- is life-threatening,
- requires hospitalisation or prolongation of existing hospitalisation,
- results in persistent or significant disability or incapacity, or
- consists of a congenital anomaly or birth defect
- is considered to be an important medical event (in the opinion of the investigator)*

* These events may jeopardise the subject or may require an intervention to prevent one of the above characteristics/consequences. Such events should also be considered 'serious'.

Procedures for recording and reporting Serious Adverse Events

All serious adverse events will be recorded by the site staff in the hospital notes, on the CRF, and the sponsor's SAE form.

All serious adverse events will need to be reported to the sponsor on a SAE form unless they fall under the category of non-reportable adverse events.

The Principal Investigator (PI) or appropriate designee is responsible for capturing SAEs on the appropriate trial specific SAE forms and reporting all SAEs to RCSI Pharmacovigilance ([contact]) within 24 hours of first becoming aware of the event (as per the RCSI Sponsor SOP on Expedited Safety Reporting). It is important to note that in the event that an SAE was not previously documented as an AE, the PI or designee must also fill out an AE form in junction with an SAE form.

SAEs will be collected from consent until the final study visit. SAEs that are related to the investigational drug and continue beyond the normal collection period (i.e., are ongoing at the time a subject exits the study) will be followed until resolution or until stabilized with sequelae. SAEs that begin after the subject's participation in the study is complete, but that the PI considers to be related to study drug, may be reported at any time. Reporting to the sponsor will be completed as per the Sponsor's Expedited Safety Reporting SOP.

Reporting SUSARs

The sponsor will notify the main REC, competent authority and marketing authorisation holder of all SUSARs. SUSARs that are fatal or life-threatening must be notified to the CA and REC within 7 calendar days after the sponsor has learned of them. Other SUSARs must be reported to the REC and CA within 15 calendar days after the sponsor has learned of them.

Development Safety Update Reports

The sponsor will provide the main REC and the competent authority with Development Safety Update Reports (DSUR) which will be written in conjunction with the trial team and the Sponsorship office. The report will be submitted within 60 days of the Developmental International Birth Date (DIBD) of the trial each year until the trial is declared ended. Any safety data from this study will be reviewed and assessed by the investigator and by reference to safety data already contained in the approved SmPC.

Annual progress reports

An annual progress report (APR) will be submitted by the Sponsor to the REC within 30 days of the anniversary date on which the favourable opinion was given, and annually until the trial is declared ended. The sponsor will prepare the APR.

Pregnancy

Any pregnancy occurring during the clinical study and the outcome of the pregnancy should be recorded and followed-up for congenital abnormality or birth defect. The Principal Investigator (PI) or appropriate designee is responsible for capturing all reported pregnancies in trial participants (or partners of trial participants) on the appropriate trial specific pregnancy form and reporting to RCSI Pharmacovigilance ([contact]) as per the RCSI Sponsor SOP on Expedited Safety Reporting.

Specific Aim 1 for Parent and Extension Study – Pulmonary Function

Forced Expiratory Volume in 1 second (FEV1)

FEV1 measured by spirometry is the most widely used evaluation of lung function in CF. As FEV1 has been used as the primary endpoint in numerous clinical trials in CF to date, it is important that the rate of FEV1 change is recorded and analyzed as a secondary endpoint in this study. Spirometry will be carried out on each subject at three monthly intervals throughout the duration of the parent study, and annually during the extension study as part of routine clinical care. Spirometry will be performed according to the American Thoracic Society (ATS) guidelines(125). Spirometry values collected as part of routine clinical care will be used for this study, rather than repeating this testing specifically for the purposes of the study. Other spirometric measures such as FVC, FEV1/FVC and FEF25-75 will be collected for inclusion in later analyses. The absolute and relative changes and rate of change in % predicted FEV1 (GLI – Global Lung Initiative) will be assessed from baseline to annual subsequent follow up periods.

Lung Clearance Index

LCI will be performed with the Exhalyzer D multiple breath washout device (Eco Medics AG, Duernten, Switzerland). The test itself is usually completed within twenty to thirty minutes (the test takes longer the more airway disease is present) and will be performed according to the European Respiratory Society / American Thoracic Society consensus statement 2013 on the performance of multiple breath inert gas washout(126).. MBW operators will be trained and certified by the team at Guy's and St Thomas' NHS Foundation Trust) under the supervision of [name]. Centralized over-reading will be completed at the RBH centre. All tests will be performed in replicate, and average values calculated for acceptable trials. LCI will be performed pre-bronchodilator in all subjects. LCI will be performed three months prior to the baseline visit and then at baseline and at 6 monthly intervals subsequently for the parent study, and annually during the extension study..

Analysis plan

The primary endpoint for LCI for the parent study will be the absolute difference in LCI in children on ETI compared the pre-treatment baseline. An interim analysis will be completed after one year of treatment, and a final parent study analysis at the end of two years. Subsequent annual and multi-annual change in LCI will be assessed during the extension study.

Risks with FEV1 and LCI Data Collection

The main foreseeable risk factor here is protocol deviation in terms of collection and timeliness of the data. FEV1 is an easy to perform test and is part and parcel of most clinical interactions with patients. Some individuals, particularly at younger ages may not be able to produce acceptable or reproducible data despite the work of trained physiologists. This we cannot control but hope to have LCI data on all these subjects, an easier to perform and more sensitive test of lung function in this setting.. For RECOVER we will seek to minimize missed data by having an LCI testing frequency of 6 monthly with a one-month window each side during the parent study, and annually thereafter. Having a site monitoring plan and continuously vetting data as it is uploaded in real time to the study database will ensure that opportunities for assessment windows are not missed. All LCI operators will be fully trained under the supervision of the GST site and all studies will be overread by the GST team, minimizing any prospect of poor-quality data.

Specific Aim 2 for Parent Study – Lung Imaging

CT Scanning

